Enrolled participants will be instructed to apply placebo (n=10) vs. active (n=20) to affected area of the occipital scalp for 4 weeks once a day (label use). Each application will be approximately 1g. Following the 4 weeks, participants will be instructed to increase application to twice daily (BID; off-label; at least 8 hours apart) for one week. Investigators will conduct a phone visit on week 5 to discuss any potential side effects with this increased dose. If tolerated, this BID regimen will be carried throughout the length of the study. If BID is not tolerated (if irritation occurs), then Bryhali will be used as a “rescue treatment” once daily for 1 week before the subject returns to BID treatment with Duobrii. If irritation recurs, subjects will be instructed to alternate Duobrii and Bryhali (ie Duobrii BID one day, followed by Bryhali QD the next day, Duobrii BID the next, and so on). Alternating topical steroid use and stepping down topical steroid strength have been known to reduce lesion count in AKN. If irritation continues to persist, then participants will be instructed to use Bryhali QD for five days a week and Duobrii BID two days a week. If participants still experience irritation with this regimen, then subjects will be transitioned entirely to Bryhali QD for the remainder of the study. In case of clearance earlier than the end of the study, participants will be instructed to continue their respective regimen to completion of the study. Gentle hair care regimen will be recommended for duration of the length of the study; with unscented shampoo & conditioner (such as Head & shoulder) and Vaseline to scalp as moisturizer to minimize risk of contact dermatitis. In addition, patients will be instructed to postpone any form of hair coloring or chemical hair processing until after the study is over.

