Participants will be followed with visits scheduled at baseline, 4 weeks, 8 weeks and 12 weeks. At each visit, participants will complete surveys regarding the severity of AKN's associated symptoms (pain, pruritus, burning etc.) as well as the dermatology quality of life index (DLQI) and numerical rating scale (NRS) surveys (Appendix B&D). In addition, photographs will also be obtained for global assessment and lesion count will be performed. The investigator will assess the treatment area for any dyspigmentation and document the % area affected within the treatment area at each visit. Tape strips will also be collected from lesional (occipital scalp) and non-lesional (frontal scalp) at Baseline and Week 12. There will be a phone call visit at week 5 to assess tolerance of medication increase and a safety follow-up visit at Week 14. Statistical analysis will be performed. Throughout the length of the study, any adverse events (AEs) related to the treatment will be recorded.

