## **RANDOMIZATION:**

Once a subject meets all the inclusion and exclusion criteria, they will be assigned a randomization number on day 0/baseline. Enrolled subjects will be randomized in a 2:1 ratio of Duobrii to placebo.

The randomization will be performed by designated research staff/personnel at the Icahn School of Medicine using a randomization generator. The subjects and assessors (sub-investigators) will remain blinded to individual treatment assignment during the study. Research staff will also be responsible for blinding of the medication.

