## **INVESTIGATIONAL DRUG SUPPLY:**

Study medication will be given to subjects at their baseline visit and subsequent visits as needed. All study medication will be stored in a secured area at 20° to 25°C.

Unblinded research personnel will dispense study drug in an opaque bag to the subject. Individuals will be instructed not to reveal the study drug to anyone except the unblinded research staff.

Investigators will instruct subjects on how to approximately measure 1g per application.

Amount of product requested:

Duobrii = (2 x 100 g tube) or 200g/subject x 20 subjects

Bryhali = (2 x 100 g tube) or 200 g/subject x 20 subjects

Vehicle= (3 x 60 g tube) or 180 g/subject x 10 subjects

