## Appendix A.

### Schedule of Events

	Screening	Baseline	W4	W5 c	W8	W12	W14 d	ET
Visit number	1	1 a	2	3	4	5	6	TBD
Informed consent	X							
Medical History	X							
Demographics	X							
Inclusion/Exclusion	X	X						
Concomitant Medications	X	X	X	X	X	X	X	X
Adverse Events	X	X	X	X	X	X	X	X
Pregnancy Test b	X	X	X		X	X		X
Administer IP		X						
Assess IP Compliance			X	X	X	X		
Return IP						X		X
DLQI		X	X		X	X		X
NRS		X	X		X	X		X
AKN severity		X	X		X	X		X
Clinical Photographs		X	X		X	X		X
Clinical Assessment/ Lesion Count		X	X		X	X	X	X
Tape strips (lesional & non- lesional)		X						
Tape strips (lesional only)						X		

- a. If screening is successful, patient will continue into their Baseline visit on same day.
- b. Where applicable, a urine pregnancy test with high sensitivity to HCG will be performed at screening and at all other visits, prior to dosing female participants of childbearing potential with Investigational Product (IP).
- c. Phone call visit
- d. Follow up visit

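### The rescue step returns an irritated subject to twice-daily Duobrii after a fixed week without requiring that the irritation has resolved, and the next scheduled contact can be 14 days later

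*Combined protocol and SAP*

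**What the plan says.** STUDY DESIGN OVERVIEW starts Duobrii or vehicle once daily for 4 weeks and then moves to BID, which the protocol marks as off-label. The first BID week ends with a check: "Investigators will conduct a phone visit on week 5 to discuss any potential side effects with this increased dose". If irritation has occurred, Bryhali is used as rescue "once daily for 1 week before the subject returns to BID treatment with Duobrii". Later steps depend on irritation coming back or continuing: alternate days, then Duobrii on two days a week, then Bryhali alone. No step carries a severity threshold, and the first return to BID carries no test of resolution.

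On contacts, the same section says "Participants will be followed with visits scheduled at baseline, 4 weeks, 8 weeks and 12 weeks", and adds: "There will be a phone call visit at week 5 to assess tolerance of medication increase". There is also a safety visit at week 14. Appendix A agrees: its week 5 column is footnoted "Phone call visit" and the next column is week 8.

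Three other parts of the protocol bear on the risk:
- SAFETY MONITORING requires the investigator to stop a subject whose safety is at risk.
- DISCONTINUATION OF TREATMENT AND WITHDRAWAL OF SUBJECTS lists a confirmed, drug-related event of at least grade 3 as a possible reason for withdrawal.
- The adverse event text under CONTRAINDICATIONS/CAUTIONS accepts events that subjects report between visits, and records severity as mild, moderate or severe.

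On blinding, RANDOMIZATION states: "The subjects and assessors (sub-investigators) will remain blinded to individual treatment assignment during the study". INVESTIGATIONAL DRUG SUPPLY states "Unblinded research personnel will dispense study drug in an opaque bag to the subject" and requests "Bryhali = (2 x 100 g tube) or 200 g/subject x 20 subjects".

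**The concern.** The rule, followed exactly, puts a subject back on the dose that caused irritation after one week whether or not the skin has settled. The protocol judged one BID week long enough to justify an active check in subjects not yet known to react. It schedules no matching check for those who have reacted and are being exposed again.

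What is at stake is mainly tolerability. Irritation, burning and pruritus are listed as common reactions to Duobrii. The step-down sequence can help only when someone learns that irritation has returned. On scheduled contacts alone, a subject who restarts at week 6 and reacts again would move to alternate days at week 8.

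**Working it through.** The check is calendar arithmetic on the dosing text and the visit schedule.

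**Inputs.** From STUDY DESIGN OVERVIEW: BID starts at week 4; phone check at week 5; Bryhali for 1 week; about 1 g per application. From the same section and Appendix A: on-treatment contacts after baseline at weeks 4, 5 (phone), 8 and 12. Assumption: irritation is acted on at the week 5 call.

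**The plan's own interval.** First BID exposure to check: (5 − 4) × 7 = 7 days, which matches the stated one week. Applications: 7 × 2 = 14, about 14 g.

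**The second exposure.**
- Restart: week 5 + 1 week of Bryhali = week 6.
- Restart to next scheduled contact: (8 − 6) × 7 = 14 days.
- Applications: 14 × 2 = 28, about 28 g.
- Ratio to the first exposure: 14 / 7 = 2.

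**With a week 7 call.** (7 − 6) × 7 = 7 days and 7 × 2 = 14 applications, equal to the first exposure.

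**If the assumption changes.** Rescue is tied to irritation, not to a date. If it began before the week 5 call, the restart would come before week 6. If it began later, the restart would come later. For example, if the same rule were applied to irritation first acted on at the week 8 visit, BID would restart at week 9 and the next scheduled contact would be week 12: (12 − 9) × 7 = 21 days. A fixed week 7 call would not cover that case.

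**Other scheduled gaps on drug, for scale.** Weeks 0 to 4: 28 days. Weeks 5 to 8: 21 days. Weeks 8 to 12: 28 days.

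**Do the general rules fill the gap?** Take a subject with mild or moderate irritation still present on day 7 of Bryhali.

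| Rule | Does it say whether to restart BID? |
|---|---|
| Rescue text | Yes: restart, on time alone |
| SAFETY MONITORING | Only if safety is at risk |
| Withdrawal section | Only at grade 3 or above, and as an option |
| Volunteered event reports | No; they bring the event to light if the subject speaks up |
| Dosing diary | No; it records doses and is reviewed at weeks 4, 8 and 12 |

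**The case against.** The strongest reply is that the protocol already manages irritation. It has a graded sequence in which each step after the first return gives less Duobrii and the last gives none. It also has a mandatory stop for safety, an option to withdraw, and a route for reports between visits. The wording of the second step, which speaks of irritation recurring, presupposes that it settled on Bryhali. This is a local reaction to a topical product in a 30-subject trial. The 28 applications describe a subject who has just been rescued yet keeps applying twice daily for two weeks without calling. Instructions on when to pause or call could also stand in the consent pages, departmental procedures or package inserts, none of which were available for this review.

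Much of this stands, and it limits the weight of the point. The 14 days and 28 applications are an upper figure for the path described, and nothing here shows that subjects lack advice elsewhere. What does not stand is the argument from wording: presupposing resolution neither requires it nor verifies it. The general rules do not govern unresolved irritation below the severe level, which is a case this pathway will meet.

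A reader might also infer that monitoring after rescue is unusually sparse for this trial. The schedule does not support that: 14 days is shorter than the other on-drug gaps of 21 and 28 days. The comparison with 7 days matters only because this subject has already reacted to the same dose.

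**Conclusion.** The concern holds in a limited form. The return to BID is not conditional on resolution. For irritation acted on at the week 5 call, the re-challenge runs up to 14 days and 28 applications (about 28 g) before a scheduled check, twice the 7 days allowed for the first BID exposure. This rests on a derived restart at about week 6, full twice-daily use, and no report from the subject in between.

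Two stronger conclusions should not be drawn. One is that an irritated subject has no protection until week 8; the general stop rules and volunteered reports do apply, and what is missing is narrower. The other is that a known share of subjects will be harmed; the documents give no irritation rate, so the number affected cannot be estimated, and counts of applications do not measure harm.

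The point concerns subject safety and clarity of instruction. It does not undermine the power calculation or the planned analyses. The change is worth considering; the trial's validity does not depend on it.

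**What to change.** 1. **Restart condition (STUDY DESIGN OVERVIEW, dosing).** Allow the return to BID only if the irritation was not severe and has resolved on Bryhali. If it is still present after 7 days, the subject does not restart BID and calls the unblinded research staff. Once it resolves, they move the subject to the protocol's next step (alternate days) instead of full BID. Severe related irritation is handled under the existing safety-stop and withdrawal rules.

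2. **Follow-up call (STUDY DESIGN OVERVIEW, visits, and Appendix A).** Add a week 7 phone call to all subjects, asking about tolerance only, so that being called does not mark the arm. For rescue that starts at another time, make the call 7 days after the restart.

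3. **Who calls.** Assign these calls to the unblinded research staff who already dispense drug. The week 5 call is assigned to investigators, and the new calls should not copy that. Bryhali is requested for 20 subjects, the size of the active arm, so a subject who mentions it to a blinded assessor could reveal the allocation.

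**Cost.** At most 20 + 10 = 30 short week 7 calls, a few more for rescue at other times, and edits to two paragraphs and one table. A few subjects will restart BID later or not at all, which slightly reduces exposure to the full regimen. No extra subjects or clinic visits are needed.

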## **PATIENT POPULATION:**

Prior to enrollment, all subjects must meet the following inclusion and exclusion criteria:

### **Inclusion criteria:**

1. Male or female subject at least 18 years of age
2. Subject is able to provide written informed consent and comply with the requirements of this study protocol
3. Subjects have AKN class I or II (less than 6.5 cm in width)
4. Subjects who are women of childbearing potential (WOCBP) must have a negative urine pregnancy test at screening and must be practicing an adequate and medically acceptable method of birth control for at least 30 days prior to Day 0 and at least 6 months after the last dose of study. Acceptable methods of birth control include intrauterine device (IUD) oral, transdermal, implanted or injected hormonal contraceptives (must have been initiated at least 1 month before entering the study); tubal ligation; abstinence; barrier methods with spermicide. If not of child-bearing potential, subjects must have a sterile or vasectomized partner; have had a hysterectomy, a bilateral oophorectomy or be clinically diagnosed infertile; or be in a menopausal state for at least a year.
5. Subject is judged to be in good general health as determined by the principal investigator.

### **Exclusion criteria:**

1. Unable to understand and provide written consent
2. Have received prior intralesional steroids for AKN within the past 6 months
3. Are using topical steroids or topical medications on their scalp within 4 weeks
4. Have used Duobrii on the scalp for AKN or other scalp disorders
5. Subject is pregnant or breastfeeding
6. Use of prior systemic medication for AKN or acne (doxycycline or isotretinoin) or hair loss in the last 6 months
7. Currently using topical minoxidil or prior use within the past 3 months
8. Have a history of other or other active scalp/hair disease or other forms of or other forms of alopecia
9. Are on systemic steroids or other immunosuppressants
10. Have a history of auto-immune disease, thyroid disorder, or hypersensitivity to steroids.

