## **INTRODUCTION:**

Acne keloidalis nuchae (AKN) is one of the chronic forms of scarring folliculitis, affecting predominantly the occipital scalp, seen mostly in men of African descent. It has been reported in a few Caucasians and other ethnic groups. The reported prevalence in African Americans ranges from 0.5% to 13.6%. The pathogenesis is yet to be elucidated. However, inflammation is central to its pathogenesis. Standard dermatologic recommendations for early or mild disease with non keloidal lesions include potent topical steroids which may be combined with topical retinoids. Early to mild disease, for the purpose of this study, includes class I and Class II AKN as defined by Lullo et al.

Combining a topical corticosteroid with a topical retinoid allows for dual mechanistic action in the management of AKN; the topical corticosteroid, provides a primarily anti-inflammatory effect and the vitamin A derivative, impairs keratinocyte proliferation. Duobrii has the advantage of being the only high potency topical steroid-retinoid combination approved by the FDA with dermatologic indication. We are, thus, proposing, the off-labeled use, of Duobrii for the management of early-mild AKN.

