### **CONTRAINDICATIONS/CAUTIONS:**

**Duobrii:** 1) Hypersensitivity to drug/class/compound 2) Pregnancy 3) Breastfeeding if applied on nipples 4) Female patients of reproductive potential 5) Pediatric patients 6) Skin infection 7) Photosensitivity 8) Sunburn 9) History of skin cancer

**Bryhali:** 1) Hypersensitivity to drug/class/compound 2) Pediatric patients 3) Skin infection

**Definition of an AE:** Any untoward medical occurrence in a subject administered a pharmaceutical product that does not necessarily have a causal relationship with the treatment. An AE can therefore be any unfavorable and unintended sign (including an abnormal laboratory finding), symptom, or disease temporally associated with the use of a medicinal (investigational) product, whether or not considered related to the investigational medicinal product.

Investigational Medicinal Product (IMP) includes the drug under evaluation and the comparator drug(s) if specified as part of the research objective, given at any time during the study. Medical conditions/diseases present before starting the drug of interest are only considered adverse events if they worsen after starting the drug of interest.

The occurrence of adverse events will be sought by non-directive questioning of the patient at each visit during the study. Adverse events also may be detected when they are volunteered by the patient during or between visits or through physical examination, laboratory test, or other assessments. All adverse events will be recorded in the study database including the following information:

1. the severity grade (mild, moderate, severe)
2. its relationship to the drug(s) of interest (suspected/not suspected)
3. its duration (start and end dates or if continuing at final exam)
4. whether it constitutes a serious adverse event (SAE)

A SAE is any untoward medical occurrence that at any dose:

- results in death
- is life-threatening
- requires inpatient hospitalization or prolongation of existing hospitalization
- results in persistent or significant disability/incapacity

- is a congenital anomaly/birth defect
- is otherwise a significant medical event

This includes any SAEs likely to arise from the trial indication or progression of underlying/concomitant illness(es) (e.g. progression of cancer in oncology trials), unless specified in the protocol as study specific exemptions.

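### Exclusion 10 bars hypersensitivity to steroids only, although Duobrii also contains a retinoid and the protocol's own caution list is wider

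*Combined protocol and SAP*

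**What the plan says.** The Introduction calls Duobrii "the only high potency topical steroid-retinoid combination approved by the FDA". It thus has two active classes, and Bryhali is supplied as the rescue and step-down product.

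Under Exclusion criteria, item 10 reads "Have a history of auto-immune disease, thyroid disorder, or hypersensitivity to steroids". It is the only inclusion or exclusion item that refers to hypersensitivity.

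Under Contraindications/Cautions, the Duobrii entry begins "1) Hypersensitivity to drug/class/compound 2) Pregnancy 3) Breastfeeding if applied on nipples". The Bryhali entry opens with the same hypersensitivity item.

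Patient Population requires every subject to satisfy the listed inclusion and exclusion criteria before enrolment. Randomization then says: "Once a subject meets all the inclusion and exclusion criteria, they will be assigned a randomization number on day 0/baseline". Neither section refers to the Contraindications/Cautions list.

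**The concern.** The entry rule screens for a reaction to one of the two active classes in the study drug, while the protocol's own list of cautions is not limited in that way. No section gives a reason for restricting the criterion to steroids.

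Earlier retinoid exposure is plausible in this population. The Introduction says that standard recommendations for early or mild disease "include potent topical steroids which may be combined with topical retinoids". Some candidates may therefore already know that they are allergic to a retinoid product or to something in its base. What is at stake is the safety of those few people: a risk that could be settled by a question at screening is instead left to the investigator's use of a separate section.

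**Working it through.** No arithmetic applies, and the plan states no figure on this point. The check is whether any written rule would stop a subject who has a known true hypersensitivity to a retinoid or an excipient and is otherwise eligible.

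1. **Exclusion 10.** It names steroids only, so it does not apply.
2. **Exclusion 3.** "Are using topical steroids or topical medications on their scalp within 4 weeks". This is a washout rule. Someone who reacted to a topical retinoid and stopped it more than 4 weeks ago passes.
3. **Exclusion 4.** "Have used Duobrii on the scalp for AKN or other scalp disorders". It catches earlier scalp use of Duobrii itself, not a reaction to another retinoid product.
4. **Exclusion 6.** It covers systemic treatment, including isotretinoin, in the last 6 months. It concerns recent use, not allergy.
5. **Inclusion 5.** "Subject is judged to be in good general health as determined by the principal investigator". A person with a contact allergy to a topical product can be in good general health. The criterion permits exclusion on judgement but does not direct it.
6. **Contraindications/Cautions.** Its hypersensitivity item does reach a retinoid reaction, through the word for class. Whether it reaches excipients is less clear. The list is not written as an entry rule, and it cannot be read as an automatic bar throughout: its fourth Duobrii item is women of reproductive potential, whom inclusion 4 admits subject to contraception and pregnancy testing. Pregnancy was carried from this list into the exclusions (item 5); hypersensitivity was carried over only in part.

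Such a subject therefore meets every named criterion.

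The next step is what happens after entry. Under Study Design Overview, treatment is once daily for 4 weeks and then twice daily. If irritation occurs on twice-daily use, the subject has one week of Bryhali and returns to twice-daily Duobrii. On recurrence, Duobrii and Bryhali alternate by day; then Duobrii is used two days a week; only then is it stopped. If a true allergy were handled as irritation, this ladder would re-expose the subject under three successive regimens that contain Duobrii. The ladder is a reasonable plan for irritation, but it is not a safeguard against allergy.

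**The case against.** The strongest reply is that the protocol already deals with this. Hypersensitivity heads the caution list for both products, the Potential Risks section refers readers to both package inserts, and nothing obliges an investigator to treat someone with a listed contraindication. The trial has a single center. Medical history is taken at screening, and eligibility is checked at screening and again at baseline. Safety Monitoring and the discontinuation section allow a subject to be stopped. The presence of women of reproductive potential on the list may show only that this item is a managed caution, not that the hypersensitivity item lacks force.

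Much of this stands. A careful investigator would probably exclude a known retinoid allergy, and a reader who inferred that the protocol offers no protection would be going too far. What does not stand is that the entry rule is therefore adequate. Enrolment is tied to the listed criteria, the one relevant criterion is narrower than the list, and withdrawal acts only after exposure.

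A second reply is that many people who stopped a topical retinoid did so because of irritation. That is correct and limits the point. Burning, dryness and irritation are listed as common reactions to Duobrii, and the step-down ladder is designed for them. Past irritation is not a reason to exclude anyone; the point concerns true hypersensitivity alone.

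A reader might also infer that a rule is missing for a subject who arrives at baseline with a sunburnt scalp. The documents do not support that as a separate defect: sunburn is on the caution list, Potential Risks already says that Duobrii is withheld until it heals, and the area is examined and photographed at baseline.

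**Conclusion.** The concern holds as a mismatch between exclusion 10 and the Contraindications/Cautions section. It is a minor safety point, worth correcting because the stated rule is too narrow and a better one is easily written.

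Its size cannot be put in numbers. The documents give no frequency of retinoid or excipient hypersensitivity in this population. Counts of criteria or active classes describe wording, and the 2:1 allocation applies to every subject, so neither measures harm. A reader might infer an effect on dropout, efficacy or power; nothing in the documents supports that, and none is claimed.

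The conclusion rests on two readings: that the inclusion and exclusion lists govern entry, as Patient Population and Randomization state, and that the caution list guides judgement without itself being a criterion. The excipient part also assumes that a subject may know of such an allergy; the documents do not list the excipients of any of the three products.

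**What to change.** Reword the last part of exclusion 10 to: *known hypersensitivity to any component of Duobrii, Bryhali or vehicle (steroid, retinoid or excipient)*. The rest of the criterion can stay. Limiting the wording to hypersensitivity keeps subjects with past irritation eligible.

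The cost is one medical-history question at the screening visit already scheduled, and possibly an occasional screen failure. The sample size, the power calculation and the planned analyses are unchanged.
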